Patient's susceptibility to DILI during treatment with anti-TB drugs is influenced by several drug- and host-related factors [102]. The most extensively studied potential causes of INH-induced DILI are related to those mechanisms. As to drug-related factors, acetylhydrazine, which is generated by NAT2, is widely considered as a crucial INH metabolite that contributes to INH-induced DILI. Given the importance of acetylation in INH metabolism, several studies have investigated into NAT2 loss of function polymorphisms as possible risk factors for DILI. In addition, advanced age [94], female gender [86], poor nutritional status [103], HBV or HCV infection [100] [104], HIV infection [78] [105], chronic liver disease, and alcoholism are environmental, physiological, and pathological factors contributing to DILI incidence. Moreover, the influencing variables differ according to racial and geographic characteristics.

Studies conducted in China demonstrated that approximately one-third of DILI patients had no symptoms, including some cases with severe liver injury [106] [107]. It has been demonstrated that screening patients for risk factors is useful in preventing disease progression, improving the outcome of therapy, and reducing mortality. However, rapid acetylators are very common in the Chinese population, so they are characterised by a lower susceptibility to develop DILI. Our patient cohort is multi-ethnic, with a prevalence of Caucasians and so a higher frequency of slow acetylator status. For this reason, our objective is to corroborate the conclusions drawn by the previous studies through the examination of our complementary data.

Outcome measures and assessments

The primary outcome is to determine the association between risk factors (drug- and host-related factors) and the incidence of DILI.

The primary outcome measures are the occurrence of anti-TB DILI (number of participants with DILI), which was defined by: 1) AST or ALT level > 5 times the ULN in patients with absence of symptoms or with total BIL level > 2 times the ULN, or 2) AST or ALT level > 3 times the ULN and total BIL level > 3 times the ULN in patients who show symptoms compatible with hepatitis.

The secondary outcome is to evaluate the characteristics of patients who first experienced anti-TB DILI. The secondary outcome measures are the prevalence of early hepatotoxicity experience.

Methods

Study design

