This is a retrospective observational study, no profit, to determine environmental, physiological, and pathological factors associated with the incidence of DILI during anti-TB treatment. Data collected from patients with confirmed tuberculosis, enrolled at the Department of Infectious Diseases of Luigi Sacco Hospital in Milan, Italy, between July 2020 and September 2023, will be analysed. Subjects were all followed up as outpatients at Tuberculosis Clinic at Luigi Sacco Hospital, some of them with previous inward stays at various hospitals in the Lombardy Region.

Study population

The following are the inclusion criteria: 1) adult patients (>18 years), 2) patient who received standard initial therapy including INH (5mg/kg), RMP (10mg/kg), and PZA (25mg/kg) for patients with active TB disease, 3) treatment with first line anti-TB drugs, including rifampicin and isoniazid for patients with latent TBI, 4) normal serum ALT and bilirubin levels, no symptoms related to abnormal liver function prior to anti-TB drug treatment and 5) informed consent. Patients with any of the following conditions are excluded from the study: 1) liver dysfunction, including biliary origin, before anti-TB therapy, 2) patients receiving non-standard treatment regimen initially (e.g., patients with severe pulmonary or extrapulmonary TB receiving large doses or more than four anti-TB drugs), 3) modified treatment regimen due to drug resistance or intolerance excluding first line anti-TB drugs, 4) lactation or pregnancy, 5) concomitant use of hepatotoxic drugs, 6) abnormal hepatic function on laboratory testing before anti-TB, 7) disease that was resistant to INH at the start of treatment or 8) patients refusing to sign informed consent.

The participants were given standard anti-TB treatment in line with international guidelines (RMP 10 mg/kg, INH 5 mg/kg), primarily administered orally, although intravenous administration was

employed for inpatients as needed, and modified to oral administration as soon as possible. The other drugs of the standard regimen included standard daily doses of PZA (15-30 mg/kg) and EMB (15-20 mg/kg).

Data collection

Data that will be collected include clinical, biochemical, and genotyping findings that are typically used in clinical practice to manage and monitor tuberculotic patients at Luigi Sacco Hospital. The complete list of parameters (host- and drug-related factors) is provided below:

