- Clinical data: age, weight, height, gender, ethnicity, hepatotoxicity or alcoholism, duration of anti-TB treatment, tuberculosis site (pulmonary or extra), adverse event, concomitant infection (HIV, HAV, HCV, HBV), past medical history, concomitant drugs. Patient's nutritional status was reported as BMI, which was calculated based on height and body weight;
- Biochemical data: ALT, AST, GGT and BIL;
- Laboratory data: NAT2 acetylator status. The acetylation status of patients will be assigned like as suggested by earlier research:
 - rapid acetylator: NAT2*4 is a wild-type allele (defined by absence of slow alleles);
 - intermediate acetylator status: carry one copy of NAT2*4 and one defective variant allele (NAT2*5, *6, *7, and *14);
 - slow acetylator: two copies of slow variant allele (NAT2*5, *6, *7, and *14).

Statistical analysis

Sample size calculation

[figure not shown]
We are planning a study of matched sets of cases and controls with 2 matched controls per case. Prior data indicate that the probability of exposure among controls is 50%, and the correlation coefficient for exposure between matched cases and controls is -0.2 [10] [108] [109] [110] [111]. If the true odds ratio for disease in exposed subjects relative to unexposed subjects is 3, we will need to study 40 case patients with 80 matched controls to be able to reject the null hypothesis that this

odds ratio equals 1 with a power of 80%, assuming that the Type I error probability associated with the test of this null hypothesis is 5%.

[figure not shown]
Parameters: Exposure in cases = 75%; Exposure in controls = 50%

Absolute difference = 25%; Relative difference = 50%; Odds ratio = 3

Sample sizes across range of OR and control exposure, with inputted values:

Number of cases required varying ratio of controls per case, other inputs constant:

We will use a nested case-control study design that takes into account time of events occurrence in sampling of controls. For each case, one or more controls are selected from the risk set at the time in which the event of interest occurred in the case. The risk set means the set of all individuals that are still “events-free” and not censored. Therefore, they are still included in the study at that time, thus, eligible to experience the event now observed in the case. As a consequence, individuals can

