be sampled as controls for more than one case and, in turn, individuals sampled as controls may subsequently become cases. Cases and controls will be matched according to baseline variables, including age, sex, and BMI, and then conditional regression analysis (a type of matched statistical analysis) will be performed to draw associations.

Data management

All data are retrieved from the patient's medical record. Variables will be entered into the eCRF by site staff, who will be trained on how to use the eCRFs and capture the data required by the protocol. The eCRF is an electronic data entry media and should not constitute the original (or source) medical record. Data derived from source documents and reported in the eCRFs should be consistent with the source documents, or the discrepancies should be explained in these source documents. The investigator must complete the eCRF for each participant. The investigator's signature on the eCRF will attest to their accuracy and completeness.

Data collected from each participant will be anonymized: each subject will be assigned a unique code so that only the investigator will be able to identify the subject. The file associating the participant's code with their identifying data will be stored separately on a password protected computer. The study database will be password protected and uploaded to a computer that is also password protected and accessible only to study personnel designated by PI. Identification of the data will be done in such a way that individuals accessing the database will not be able to trace the identity of the subjects in any way.

The study will involve statistical calculations on collected data using literature standard methods to identify and correlate variables (Chi-square, Fisher's exact, Mann-Whitney U-test, conditional regression). The results will be published in medical journals and presented at conferences. Study data will be retained for 7 years starting from the study's conclusion. Data processing will be done in strict compliance with GDPR and any applicable national legislation.

Potential Benefit of the Study

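### The primary question covers all drug- and host-related risk factors without rank, but the sample size, 80% power and 5% error apply to one exposure that is never named

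*Protocol*

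**What the plan says.** The protocol's section on outcome measures and assessments states: "The primary outcome is to determine the association between risk factors (drug- and host-related factors) and the incidence of DILI". The wording is plural and gives no order of importance. Besides NAT2 acetylation, Rationale and Aims names these contributors to DILI: "advanced age [94], female gender [86], poor nutritional status [103], HBV or HCV infection [100] [104], HIV infection [78] [105], chronic liver disease, and alcoholism". The Data collection section adds a longer list under the words "The complete list of parameters (host- and drug-related factors) is provided below".

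The sample size section describes something narrower. It opens: "We are planning a study of matched sets of cases and controls with 2 matched controls per case". It continues: "Prior data indicate that the probability of exposure among controls is 50" per cent, and "the correlation coefficient for exposure between matched cases and controls is -0.2". With an odds ratio of 3 and 80% power it arrives at 40 cases and 80 controls, "assuming that the Type I error probability associated with the test of this null hypothesis is 5" per cent. The exposure is not identified there or elsewhere. Later in the same section: "Cases and controls will be matched according to baseline variables, including age, sex, and BMI".

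**The concern.** The primary outcome asks about many factors, while the calculation supports one test of one odds ratio. A reader cannot tell which association has 80% power, and nothing says how the 5% is used across factors that all count as primary.

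Two misreadings follow. A significant result on any one factor could be reported as a positive primary finding, although there were several chances to obtain one. A non-significant result for an uncommon factor, such as a viral co-infection, could be read as absence of risk under a stated 80% power that was never calculated for it. The protocol intends its results to inform DILI prevention and risk-factor screening, so both errors would matter.

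**Working it through.** **1. The protocol's own figure.** Inputs from the sample size section: control exposure p0 = 0.50, odds ratio ψ = 3, M = 2 controls per case, correlation φ = −0.2, error 5% (two-sided assumed, since the protocol does not say), power 80%. The method is the Dupont formula for matched case-control studies.

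- Case exposure: p1 = p0ψ / (1 + p0(ψ − 1)) = 1.5/2 = 0.75, as stated.
- Probability that a control is exposed: 0.4423 if the case is exposed, 0.6732 if not.
- Probability that a set has one or two exposed members: t1 = 0.3433, t2 = 0.4833.
- Expected exposed cases per set: under the null, e1 = Σ m·t_m/(M+1) = 0.4366; under the alternative, eψ = Σ m·t_m·ψ/(mψ + M − m + 1) = 0.6202. The difference is 0.1836.
- Variances: v1 = 0.1837 (root 0.4286) and vψ = 0.1416 (root 0.3763).
- n = (0.8416 × 0.3763 + 1.9600 × 0.4286)² / 0.1836² = 39.69, so **40 cases**.
- Power at 40 = Φ[(√40 × 0.1836 − 1.9600 × 0.4286) / 0.3763] = **80.3%**.

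The stated size reproduces for one exposure tested once.

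**2. How many named factors can be tested.** Rationale and Aims names NAT2, age, sex, nutritional status, HBV or HCV, HIV, chronic liver disease and alcoholism. Age, sex and BMI are matching variables, so their association with DILI cannot be estimated from the matched sets. Liver dysfunction and abnormal hepatic function before treatment are exclusions, which largely removes chronic liver disease. What remains is NAT2, HBV/HCV, HIV and alcoholism: k = 4, or k = 5 with HBV and HCV separate.

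**3. Error and power over that set.** The chance of at least one false positive at 5% per test, if all factors are null and the tests independent, is 1 − 0.95^k. Power under a Bonferroni split uses the step 1 formula with the critical value for 0.05/k.

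| k | Chance of ≥1 false positive | Split level | Critical value | Power per factor, 40 cases |
|---|---|---|---|---|
| 4 | 18.5% | 0.0125 | 2.498 | 59.5% |
| 5 | 22.6% | 0.0100 | 2.576 | 56.0% |

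For k = 4: Φ[(1.1612 − 2.498 × 0.4286)/0.3763] = Φ(0.241) = 59.5%. These powers keep the protocol's 50% exposure, odds ratio 3 and correlation −0.2.

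**4. Uncommon exposures, each tested at an unadjusted 5%.** The protocol gives no prevalence by factor, so 5% and 10% of controls are assumptions. At an odds ratio of 3, a correlation of −0.2 is impossible there: the implied probability of an exposed control given an exposed case is −0.060 at 5% prevalence and −0.004 at 10%. The range below therefore uses correlations from 0.2 to 0.

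| Control prevalence (assumed) | Power at OR 3, φ = 0.2 to 0 | Detectable OR at 80% power, φ = 0 |
|---|---|---|
| 5% | 31% to 38% | 5.2 |
| 10% | 48% to 57% | 3.9 |

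**The case against.** The strongest reply is that the protocol makes no claim about the whole set of factors. It attaches the 5% to one null hypothesis and the 80% to one odds ratio, and both hold for any exposure that fits the inputs. That is correct, and it limits the point: the calculation is not wrong, it answers a narrower question than the primary outcome asks. A multiplicity procedure could also sit in an SAP that is not shown. That would not close the gap, because the protocol itself fixes both the primary outcome and the sample size and names no primary exposure. The protocol also announces a table of sample sizes across odds ratios and control exposures, which is not shown. It may cover other prevalences, but the planned size rests on the single 50% scenario.

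Three stronger readings are tempting and are not supported:

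- A reader might count about eleven unmatched items in the data collection list and infer 1 − 0.95^11 = 43% false positives. That list also contains outcome measurements such as ALT, AST and bilirubin, and nothing makes each item a primary hypothesis. Nor is a false positive more likely than not, and the calculation requires every factor to be null, whereas the study aims to corroborate earlier findings.
- A reader might infer that power fails at any prevalence other than 50%. At the protocol's own correlation of −0.2 and odds ratio 3, power at 20% prevalence is 80.7%, and it stays at or above 80% from about 20% to 50%.
- A reader might infer an overloaded regression with all factors in one model. The protocol says only that conditional regression will be used and proposes no such model.

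**Conclusion.** The concern holds in this limited form. The stated 80% power and 5% error are valid for one exposure meeting the stated inputs; they do not describe the primary outcome as written. Over the four or five named factors that can be tested, the chance of at least one false positive is about 19–23% without adjustment, or power per factor is about 56–60% with a Bonferroni split. For exposures in 5–10% of controls, power at an odds ratio of 3 is about 31–57%.

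The error figures assume independent tests and that all factors are null. The factor count is a reading of the rationale after matching and exclusions. The low prevalences are assumed, not taken from the protocol. A study of several risk factors is legitimate; what needs correcting is calling them all primary under a power statement that belongs to one.

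**What to change.** - Name one primary exposure, tested at 5%. NAT2 slow acetylator status against intermediate plus rapid is the natural candidate: the rationale rests the study's added value on the cohort's acetylator profile, and the data collection section defines the categories.
- State that the 40/80 calculation and its 50% exposure refer to that factor, and give the basis for the 50%.
- Label all other factors secondary or exploratory, report them with confidence intervals, and make no claim of absence from a non-significant result.
- State that the 80% power does not extend to them, and give the detectable odds ratio for uncommon exposures (about 5.2 at 5% and 3.9 at 10% of controls, zero correlation).

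The cost is mostly wording, with two real consequences. The other factors lose primary status. The 50% must also be justified for the named exposure, because the protocol gives no slow-acetylator frequency for this cohort. If the true figure were 60% or 70%, power at 40 cases, odds ratio 3 and correlation −0.2 would be 72.5% or 59.1%, and the required number of cases would rise to 47 or 61.

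### The primary DILI case definition drops symptomatic patients whom it would count as cases if they had no symptoms

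*Protocol*

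**What the plan says.** Under Outcome measures and assessments, the primary outcome measure is the occurrence of anti-TB DILI, expressed as the "number of participants with DILI". A patient qualifies by either of two clauses:

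- Clause 1 reads "AST or ALT level > 5 times the ULN in patients with absence of symptoms or with total BIL level > 2 times", where the bilirubin multiple, like the enzyme multiple, refers to the upper limit of normal.
- Clause 2 applies when the symptoms point to hepatitis and reads "AST or ALT level > 3 times the ULN and total BIL level > 3 times the ULN in patients who show symptoms".

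Nothing in that section says whether the criteria must be met at a single time point or may be met at different times within one episode.

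The same rule feeds the nested case-control design described under Statistical analysis. The definition there opens with "The risk set means the set of all individuals that are still"; in substance it covers people who are free of the event and not censored. The protocol describes such people as "eligible to experience the event now observed in the case". It also notes that "individuals sampled as controls may subsequently become cases".

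The opening background text describes the definition used in most reports: AST or ALT at 3 times the ULN when symptoms are present and 5 times when they are absent, with no bilirubin condition.

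**The concern.** A liver-injury definition that takes symptoms into account would be expected to ask for less laboratory evidence when symptoms are present, as the protocol's own background describes. Here one combination runs the other way: with the same laboratory values, adding hepatitis symptoms removes the patient from the case group. The wording of clause 1 is also ambiguous, because it is unclear what the phrase about bilirubin above 2 times the ULN attaches to.

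Two things are at stake. First, patients who stay in the affected combination throughout their episode would not be counted, so the primary count can be too low. Second, unless they are censored or excluded, they would formally remain event-free and could be drawn as controls after their episode. That can dilute odds ratios for risk factors they share with counted cases. Before the episode they are legitimate controls.

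**Working it through.** **Truth table.** Cross symptoms (no, yes) with AST/ALT (≤3, >3 to 5, >5 × ULN) and bilirubin (≤2, >2 to 3, >3 × ULN). This gives 2 × 3 × 3 = 18 cells, or 9 laboratory pairs each seen with and without symptoms. A cell is a case if clause 1 or clause 2 is met. Clause 1 was read in four ways:

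| Reading of clause 1 | Case cells of 18 | Pairs that are a case without symptoms and a non-case with them |
|---|---|---|
| A: AST/ALT >5 and (no symptoms or bilirubin >2) | 6 | 1 of 9 |
| B: (AST/ALT >5 and no symptoms) or bilirubin >2 | 13 | 1 of 9 |
| C: AST/ALT >5 with neither symptoms nor bilirubin >2 | 3 | 1 of 9 |
| D: no symptoms and (AST/ALT >5 or bilirubin >2) | 9 | 5 of 9 |

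Under A, B and C the single inverted pair is AST/ALT >5 with bilirubin ≤2. The steps for that pair are:

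- No symptoms: clause 1 is met, so the patient is a case.
- Symptoms: neither alternative in clause 1 is met, and clause 2 fails because bilirubin is not above 3. The patient is a non-case.

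D inverts the same pair and four more: (≤3, >2 to 3), (≤3, >3), (>3 to 5, >2 to 3) and (>5, >2 to 3). Replacing the printed *or* in clause 1 by *and* removes the inversion at bilirubin ≤2, but creates one at AST/ALT >5 with bilirubin >2 to 3.

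**Ambiguity.** A, B and C agree on 8 cells (3 cases, 5 non-cases) and disagree on 10 of 18. Adding D leaves those 10 unchanged. If B and D are set aside, A and C still disagree on 3.

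**Size of the smallest repair.** Making a symptomatic cell a case whenever its asymptomatic twin is one changes 1 of 18 cells under A, B or C, and 5 under D.

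**Effect on the analysis: illustration only.** The inputs from Sample size calculation are 2 controls per case, 50% exposure in controls, 75% in cases, odds ratio 3, exposure correlation −0.2, 5% type I error and 80% power. Dupont's matched formula, two-sided, gives 39.69, so 40 cases and 80 controls, as stated. With 40 sets the power is 80.3%.

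Further inputs are assumed:

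- Nobody is censored or excluded.
- Two-thirds of true cases have symptoms. This follows from the statement in Rationale and Aims, about studies in China, that "approximately one-third of DILI patients had no symptoms".
- A share s of 0.1 to 0.8 of symptomatic cases stay in the uncounted combination (bilirubin ≤2). The protocol gives no source for this range.
- Half of the sampling time falls after the episode.
- Missed cases have 75% exposure.

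The missed fraction is m = (2/3)s, which is 0.067 to 0.533. With incidence I, the contaminated share of controls is c = 0.5·I·m / (1 − I + I·m). Control exposure is 0.5(1 − c) + 0.75c, and the observed odds ratio is 3 divided by the odds of that exposure.

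| I (from the background range) | c | Odds ratio | Power |
|---|---|---|---|
| 5% | 0.17% to 1.37% | 2.995 to 2.96 | 80.2% to 79.2% |
| 28% | 1.26% to 8.59% | 2.96 to 2.75 | 79.3% to 72.6% |

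The 28% covers all hepatotoxicity under mixed thresholds, so the second row is a corner and not an estimate.

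**The case against.** The clauses are alternative routes to one outcome, and no patient is declared both a case and a non-case. In the strict sense they do not contradict each other, and that stands. The defect is that the combined rule is not monotone in symptoms and is ambiguously worded. The background definition does not bind the study, which may have meant to be stricter. That is possible, but the protocol gives no reason why symptoms should remove a patient from the case group.

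The practical effect is not demonstrated. No cohort patient is shown to fall in the combination, and a patient who meets a clause at another point in the episode may still be counted. The control-contamination route is conditional: risk sets are limited to uncensored people still eligible for the event, and Potential Benefit of the Study describes prompt drug withdrawal. The exclusion for "modified treatment regimen due to drug resistance or intolerance excluding first line anti-TB drugs" may also remove some of these patients. All of this stands, so the power figures carry no weight in the conclusion. None of it restores a patient whom the rule leaves uncounted.

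Finally, the outcome section uses the past tense for the definition, so classification may already have begun. That affects the cost of the repair, not the need for it.

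**Conclusion.** The concern holds. Under all four readings tested, AST or ALT above 5 times the ULN with bilirubin at or below 2 times is a case without symptoms and a non-case with them, and nothing else in the protocol closes the gap. The bilirubin condition in clause 1 is also unclear enough that 10 of 18 combinations depend on the reader. This must be fixed because the rule that defines the primary outcome is wrong as written, not because a large effect has been shown.

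The number of patients affected cannot be computed, since the protocol gives no joint distribution of symptoms and bilirubin. The undercount is zero if nobody stays in the combination, and control contamination is zero if all such patients are censored or excluded.

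**What to change.** Before records are classified and risk sets drawn:

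1. Reconcile the two clauses of the research case definition so that symptoms can never turn a case into a non-case. In particular, a symptomatic patient with AST or ALT above 5 times the ULN is counted just as an otherwise identical asymptomatic patient is.
2. Keep the bilirubin branch, and state what the condition of bilirubin above 2 times the ULN in clause 1 is meant to add. This settles which reading applies.
3. State whether the criteria are judged at one time point or over the episode.
4. Report how many patients change status relative to the present wording. A count is enough; no second matched analysis is needed.

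The cost is a rewording applied when the 2020 to 2023 records are classified. Control sampling is described in the future tense, so the change can come before it. If classification has begun, some records will need reclassifying. AST, ALT and bilirubin are already collected, and clause 2 already requires symptom status. However, Data collection lists symptoms only indirectly, through adverse events, so the count may be incomplete where symptoms were not recorded. The change concerns research classification only and alters no treatment decision.
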